12. REGULATORY ASPECTS

Notification/application to Relevant Competent Authorities

According to the individual country law/regulation, the study will not be initiated before it has

been approved by the relevant Competent Authorities and Ethics Committee.

13. FINANCING AND STUDY INSURANCE

Bioprojet will cover the additional costs related of this study. These costs will be defined and

agreed before the start of the study. A financial agreement will be made between the parties,

institution, investigator and the sponsor, in accordance with each administrative procedure.

Bioprojet will contract a specific insurance policy for the coverage of the patients in conformity

to the National regulation.

14. PUBLICATION POLICY

All information resulting from the study will be considered as confidential, and must not be divulged without the sponsor's prior agreement.

The study results may be published or presented by the investigator or analysis experts, in collaboration with Bioprojet, with the Bioprojet's written permission. Bioprojet may use the study results for any publication or communication, with the written agreement of the investigator, or the analysis experts if they are quoted.

15. CALENDAR FORECAST

- First patient visit is scheduled in Q1 2016.
- For each patient, the study will last 13 weeks, of which a 8-week treatment period with the investigational medical product or placebo.
- The end of study (double blind period) is expected in Q1 2022.

16. APPENDICES

Appendix 1: Ullanlinna Narcolepsy Scale (UNS)

[figure not shown]
Appendix 2: Epworth sleepiness scale adapted for children and adolescents (CASS)

Appendix 3: Paediatric Daytime Sleepiness Scale (PDSS)

[figure not shown]
Appendix 4: Childhood Depression Inventory (CDI)

Appendix 5: Clinical Global Impression (CGI)

Appendix 6: Sleep Diary

[figure not shown]

BIOPROJET Version 3.0
Protocol P11-06/ BF2.649 September 30th, 2020
EudraCT number: 2013-001506-29

# 1 List of abbreviations and definition of terms

Abbreviations	Definitions
AEs	Adverse events
ANCOVA	Analysis of Covariance test
BMI	Body mass index
CASS	Child and Adolescent Sleepiness Scale
CDI	Childhood Depression Inventory
CGI-C	Clinical Global Impression of Change
CGI-S	Clinical Global Impression of Severity
CNS	Central nervous system
CRF	Case report form
CRO	Contract Research Organization
CSR	Clinical Study Report
C-SSRS	Columbia-Suicide Severity Rating Scale
DSM-IV	Diagnostic System Medical, fourth version
DSMB	Data Safety Monitoring Board
ECG	Electrocardiogram
EDS	Excessive Daytime Sleepiness
FAS	Full Analysis Set
GCP	Good Clinical Practice
ICH	International Conference on Harmonisation
ICSD	International Classification of Sleep Disorders
IEC	Independent Ethics Committee
IMP	Investigational Medicinal Product
KLS	Keyrus Life Science
MAR	Missing At Random
MCMC	Markov chain Monte Carlo
MD	Missing Data
MI	Multiple Imputation
MNAR	Missing Not At Random
MSLT	Multiple Sleep Latency Test
MWT	Maintenance of Wakefulness Test
OSA	Obstructive Sleep Apnoea syndrome
PDSS	Pediatric Daytime Sleepiness Scale
PPS	Per Protocol Set
PS	Paradoxical sleep
PSG	Polysomnography
REM	Rapid Eye Movement
RS	Randomised Set
SAF	Safety Set
SAE	Serious Adverse Event
SD	Standard Deviation
TEA-Ch	Test of Everyday Attention for Children
UNS	Ullanlinna Narcolepsy Scale
UNS-CTP	Ullanlinna Narcolepsy Scale - Cataplexy
UNS-EDS	Ullanlinna Narcolepsy Scale - Excessive Daytime Sleepiness
TLG	Tables, Graphs and Listings
WRC	Weekly rate of Cataplexy

## 2 Introduction

This document describes the frame of the statistical analyses that will be conducted for the study P11-06/BF2.649: A double blind, multicenter, randomized, placebo-controlled trial to evaluate safety and efficacy of pitolisant in children from 6 to less than 18 years with narcolepsy with/without cataplexy, followed by a prolonged open-label period.

This Statistical Analysis Plan has been written in agreement with:

- The Clinical Study Protocol Version 3.0 dated September 30th, 2020
- The Case Report Form (CRF) Version 7.0 dated December 16th , 2020

This document is the reference document for all the statistical analyses of **the blind part** of this study. The purpose of this document is to describe:

- The characteristics of the study as defined in the protocol: objectives, design and conduct of the study
- The criteria/variables analysed and the derived variables to be created.
- The planned statistical analysis and the methodology to be used.

# 3 Study description

According to guidelines published by European task force [Billiard M et al, Eur J Neurol. 2006]i, management of narcolepsy with or without cataplexy relies on several classes of drugs, namely stimulants for EDS, antidepressants for cataplexy and hypnosedative drugs for disturbed nocturnal sleep [Dauvilliers Y et al, Clin Neurophysiol. 2003]ii.

Narcolepsy is a neurological disorder frequently occurring from childhood and persisting through adolescence and adulthood. Individuals suffering from narcolepsy exhibit excessive daytime somnolence, sleep attacks, cataplexy, dysomnia, metabolic perturbations including weight gain, and problems in social interaction and academic performance. The prevalence of narcolepsy in childhood is not known but can be estimated from adult studies to be greater than 20-60 per 100,000 in Western countries. (Handb Clin Neurol. 2013; 112:839-45. doi: 10.1016/B978-0-444-52910-7.00003-9. Pediatric narcolepsy: clinical and therapeutical approaches. Lecendreux M.)

Narcolepsy occurs during childhood in combination with cataplexy in one-third of the subjects. Symptoms may develop rapidly over a few weeks or months, with excessive daytime sleepiness and cataplexy being the most dramatic and observable symptoms. It can be secondary to brain tumors or several rare diseases, but in most cases narcolepsy with or without cataplexy is a primary condition, better explained by the selective loss of hypocretin neurons in posterolateral hypothalamus. (Paediatr Drugs. 2014 Oct; 16(5):363-72. doi: 10.1007/s40272-014-0083-3. Pharmacological management of narcolepsy and cataplexy in pediatric patients. Lecendreux M)

Pitolisant is an H3R inverse agonist that promotes significantly vigilance in narcoleptic patients. The results obtained in the previous studies showed that BF2.649 reduced significantly the diurnal somnolence compared to placebo confirming its wakening effect against EDS with a gain of 4.5 points on the ESS and demonstrating its anti-cataplectic effect when administrated on an individual titration scheme established on basis of individual benefit/tolerance ratio. Phase III studies compared pitolisant to Placebo and to modafinil the current first line treatment of narcolepsy: the results are in favour of pitolisant compared to Placebo and do not show any statistically significant difference compared to modafinil.

The purpose of this study is to check whether Pitolisant (BF2.649) is efficient to decrease EDS and the supportive symptoms of narcolepsy in children from 6 to less than 18 years of age, as well as to reduce the number of cataplexy crises (for patients with cataplexy).

# 3.1 Study objectives

## 3.1.1 Primary objective

The primary objective of this study is to compare pitolisant to placebo, with regard to Excessive Daytime Sleepiness (EDS) on the one hand, and to the number of cataplexy episodes, if any, on the other hand.

This trial will characterize the efficacy of pitolisant (5-, 10-, 20-, 40 mg/d in Double Blind Period and 5-, 10-, 15-, 20-, 30-, 40 mg/d in Open Label Period) compared to placebo in showing an incremental improvement to the situation particularly in terms of a reduction of EDS as measured by the Ullanlinna Narcolepsy Scale (UNS), and also on the number of cataplexy episodes, if any.

# 3.1.2 Secondary objectives

The secondary objectives of this study are to assess, between groups:

- Changes in EDS measured:
  - by the maintenance of wakefulness test (MWT)
  - by the Paediatric Daytime Sleepiness Scale (PDSS)
  - by the Child and Adolescent Sleepiness Scale (CASS)
- Changes in number of cataplexy episodes per weeks, recorded in sleep diary by patient and/or parent/teacher;
- Severity of EDS and cataplexy measured by the clinical Global Impression of severity and change
- Differences in weekly frequency of cataplexy episodes, recorded in sleep diary by patient and/or parent/teacher;
- Changes in the TEA-Ch test
- Comparison in withdrawal symptoms questionnaire
- Comparison in patients' Global Opinion on treatment effect at the end of treatment.
- To check the clinical and biological tolerance of pitolisant.

## 3.2 Study design

This is a double blind, multicenter, randomized trial followed by a prolonged open-label period. This SAP only deals with the blind part.

## 3.3 Study plan

## 3.3.1 Study duration

The expected duration of patient participation from the screening visit (V0) until the final blind visit (V8) will be 13 weeks, including:

- Baseline period without investigational treatments (from V0 to V2): 4 weeks,
- Low and medium dose titration phase (from V2, randomisation, to V3): 2 weeks,
- Individual dose adjustments (from V3 to V5): 2 weeks,
- Stable dose phase (from V5 to V7): 4 weeks,
- 1-week study drug wash out (placebo) after study drug discontinuation.

During the blind phase, the patient will be followed in an ambulatory way by 9 visits (8 visits during double blind period and 1 visit for the single blind period) on the site.

## 3.3.2 Data collected

A detailed list of procedures performed at each visit is presented in table1.

# Table 1: Study Schedule measurement in blind period

Visits	Screening V0 	VI	Inclusion V2	V3	V4	V5	V6	Endpoint V7	T1- Phone Contact	V8	Premature withdrawal 
Study day	D-28	D-14	D0 ±2	D14 ±2	D21 ±2	D28 ±2	D49 ±2	D56 ±2	D59 ±1	D63 ±2	+ 5
Informed consent	X	X*									
Narcolepsy history, Medical history and prior medications	х	X									
Physical examination, vital signs	Х	Х	Х	Х	X	Х	Х	Х		Х	Х
ECG 		х	X	Х	X	Х	X	х		Х	Х
Lab tests 		х						Х			X
Selection criteria	Х	Х	Х		ý						
Polysomnography - MSLT			X7								
MWT			Х					х			
PDSS		Х	Х	Х	Х	Х	Х	Х		Х	Х
CASS		Х	Х	Х	Х	Х	X	х		Х	Х
Ullanlinna narcolepsy scale		Х	Х				Х	Х			Х
TEA-Ch		X					X				
CGI EDS + CGI Cataplexy		х	Х				Х	Х		Х	X
Childhood Depression Inventory (CDI)		Х			Х		X			Х	Х
C-SSRS		Х	Х	Х	Х	Х	Х	Х		Х	Х
Adverse events and concomitant medications	Х	х	X	Х	X	X	Х	Х	х	Х	х
Dispensation of study drugs 			X	Х	X	X		Х			
Drug accountability				Х	X	X	Х	X		Х	X
Withdrawal symptoms questionnaire (DSM IV)									X	Х	х
Patients' global opinion 								X			Х
Sleep diary delivery	Х	Х	X	X	Х	X	X	Х			
Sleep diary retrieval 		Х	Х	Х	X	X	Х	X		Х	Х

- 1 The 4-week escalating dosage phase is followed by a 4-week stable-dose period during which the dose will be 5-, 10-, 20, or 40 mg/d of pitolisant or placebo
- 2 Complete biological examination including: Red Blood Cells, White Blood Cells (differential count, absolute value), Hemoglobin, haematocrit, Mean corpuscular volume (MCV), platelet count, quick time, sodium, potassium, chloride, creatinine, alkaline phosphatases, urea, alanine aminotransferase (ALAT), aspartate aminotransferase (ASAT), gamma glutamyl transpeptidase (GGT), total bilirubin, glucose, triglycerides, total cholesterol, βHCG (only for pubescent female). Dipstick urinalysis. A urinary drug testing (test applicable to patients from 12 years).
- 3 The premature withdrawal from the study should be followed by a visit performed within a maximum of 5 days after the last dose of study drug.
- 4 The sleep diary has to be completed every evening from V0 to V8.
- 5 The global opinion will be reported by patient if able to express himself. If not will be reported either by parents or teachers.
- 6 ECG: calculation of the QTcF value and delta of QTcF values between baseline ECG and ECGs performed at each subsequent visits.
- 7 Polysomnography-MSLT will be performed the day preceding V2, unless performed during the previous year.
- 8 V0 is required to ensure proper selection of patients under prohibited medications. For patients not using any prohibited medication study or patients cataplectic not using anticataplectic treatments may start at V1.
- \* Inform consent will be signed once either at V0 or V1 when applicable.

## 3.3.3 Administration of IMPs

When the patient receives his/her study number, the corresponding investigational treatment identified by the treatment number will be allocated to the patient according to the randomization list established by an independent company and managed by Interactive Web Response Services (**IWRS**) according to randomization.

The study treatment will be dispensed only under the restricted condition defined in the protocol. The treatment will be dispensed only by the investigator under his direct supervision or the pharmacist. Time of dispensation and initials of the person dispensing the drug will be recorded in the CRF. The tear-off label of each pack will be stuck on the prescription form.

At each visit the compliance to the treatment will be investigated. Details of the quantities of each medication dispensed will be entered into the accountability form. The patients will be asked whether the investigational treatment is taken as prescribed. If not, any change in the treatment and the number of forgotten tablets will be recorded in the case report form (CRF). In addition, the number of remaining tablets in the pillbox will be counted and compared to the theoretical number. Any mismatch will be investigated with the patient.

# 3.4 Changes in the conduct of the study

The last version of the protocol is version 3.0, dated September, 30th 2020. The original protocol was amended 3 times. The list of exhaustive changes is described in the summary of changes from each protocol amendment.

## 4 Statistical methods

## 4.1 General statistical considerations

## 4.1.1 Software used

All statistical analyses will be performed with the SAS® software version 9.4 or higher.

## 4.1.2 Descriptive statistics

Continuous variables will be described using: number of non-missing observations (N), number of missing observations (Nmiss), arithmetic mean (Mean), standard deviation (SD), minimum (MIN), quartile 1 (Q1), median (Median), quartile 3 (Q3) and maximum (MAX). MIN, Q1, Median, Q3 and MAX will be given at the data number of decimal points. Mean and SD will be given at 1 additional decimal point. 95% two-sided confidence interval (CI) will be calculated when appropriate using the standard method (Standard normal distribution).

Categorical variables will be presented using N, Nmiss and percentages (%). Missing data or unknown responses will not be included in the denominator for the calculation of percentages but will be presented in the results tables. Proportions will be displayed with one decimal.

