# 4.2 Sample size calculation

(ICH E3; 9.7.2. ICH E9; 3.5)

The initial protocol was based in assuming a Pearson correlation coefficient of R=0.5 between prebaseline and final values of PDSS, two pre-baseline measurements [(V1+V2)/2] and two post-baseline measurements [(V6+V7)/2]. A standardized mean difference of at least 0.5 (considered as the minimum clinically significant difference) will be detected at a two-sided 0.05 confidence level with a power of at least 0.8, when the sample size/group is at least 20 and 40 patients for control and tested drug groups, respectively.

At a later stage, UNS measuring EDS and cataplexy was used as the primary outcome instead of the PDSS. As UNS was expected with a residual variability larger than PDSS, the initial power of .75 judged as too small, a recalculation of the sample size was performed on a standardized mean difference of 0.5 on the UNS (considered as the minimum clinically significant difference), a ratio 1:2, and a correlation R=0.4. Under these assumptions, and ANCOVA test at 0.05 two-sided confidence level, the probability of a significant effect will be found with a power of 0.85 when the sample size exceeds 36+72 patients for control and tested drug groups, respectively, thus a total of 108 patients.

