# Safety Set (SAF):

All patients who receiving at least one treatment dose.

4 subgroups will be used in some analyses, according to:

- Age at baseline ([6-11], [12-18[)
- Sex
- BMI at baseline (underweight , normal, overweight and obese)
- Type of narcolepsy (Type 1 or Type 2)

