## 4.5.3.1.2 Sensitivity and other analyses

Sensitivity analyses will be performed to assess the robustness of the primary analysis results:

- Using MNAR option of the MI imputation (removing the treatment effect in the imputation model of the partially-complete data sets).
- Using the same model as for the primary analysis will be performed with the center as fixed effect instead of random effect.
- Using the same model as for the primary analysis will be performed with in addition the oxybate sodium intake and treatment-by- oxybate sodium intake interaction as fixed effects.
- Using an observed Cases analysis: The same model as for the primary analysis will be performed in patients having a value of UNS total score at V6 or V7 (i.e. in this case analysis restricted to completers the double blind period).
- Using the same model as for the primary analysis will be performed by actual treatment group, only if actual group is different from randomized group.

The same statistical elements to estimate the treatment effect as for primary analysis will be provided.

In addition, value and change from baseline descriptive statistics at each visit by treatment group will be provided, overall and by subgroups.

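### The SAP's rule for descriptive 95% confidence intervals of means uses the normal quantile although the SD is estimated, so any such interval is too narrow: trivially for whole arms, more so in small cells if intervals are printed there

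*SAP*

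**What the plan says.** The general rule is in SAP section 4.1.2, in the paragraph on continuous variables: a two-sided 95% interval, given only where judged appropriate, is calculated "using the standard method (Standard normal distribution". The same paragraph lists the statistics reported by default: counts, mean, SD, minimum, quartiles and maximum. A confidence interval is not on that list. The section names no t quantile and no minimum cell size, and no other section of the SAP changes the rule.

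Section 4.3 defines the subgroups: "4 subgroups will be used in some analyses, according to" age (two classes), sex, BMI ("BMI at baseline (underweight , normal, overweight and obese") and narcolepsy type ("Type of narcolepsy (Type 1 or Type 2"). For the UNS, section 4.5.3.1.2 plans "value and change from baseline descriptive statistics at each visit by treatment group will be provided, overall and by subgroups". That sentence does not mention confidence intervals. The table shells are a separate file (sections 5 and 6).

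Section 4.2 gives the planned arm sizes: "36+72 patients for control and tested drug groups, respectively, thus a total of 108 patients".

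**The concern.** The standard normal quantile gives an exact 95% interval for a mean only when the SD is known. Here the SD is estimated from the same patients, and the correct pivot is Student's t. Using 1.96 always errs in the same direction: the interval is too short and precision is overstated.

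With 36 or more patients the loss is negligible, but it grows quickly as n falls. The plan divides a placebo arm of 36 by four BMI classes and by narcolepsy type, so some cells could be small. A programmer who follows 4.1.2 literally would apply 1.96 wherever a descriptive interval is produced. If that includes small paediatric subgroups, their means would look better determined than they are.

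**Working it through.** **The plan's own figure.** The 97.5% quantile of the standard normal is 1.960. With a known SD, mean ± 1.960·SD/√n covers exactly 95%, so the nominal level is reproduced under that condition.

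**With an estimated SD and normal data.**
- True coverage of the interval as written = P(|T| < 1.960), where T has n-1 degrees of freedom.
- Extra width needed = t(0.975, n-1)/1.960 - 1.

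**Which cell sizes to look at.**
- Whole arms, SAP 4.2: 36 placebo and 72 pitolisant.
- Smaller age class: Protocol 3.4 aims for at least 40% in each, so 0.40 × 36 ≈ 14 placebo patients if the balance carries over to each arm. The same 40% target for gender within age group gives about 14 for the smaller sex group.
- BMI class: 36/4 = 9 placebo patients on average, and fewer in a rare class. No distribution is given (assumption).
- Narcolepsy type: no distribution is given. Taking cataplexy as a proxy for type 1 (assumption), the 80% in Protocol section 1 leaves 0.20 × 36 ≈ 7 placebo patients in the smaller group. The one-third in SAP section 3 leaves 36/3 = 12.
- n = 5 and n = 3 are shown only for illustration.

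| n | t(0.975, n-1) | True coverage with 1.960 | Extra width under t |
|---|---|---|---|
| 72 | 1.994 | 94.6% | 1.7% |
| 36 | 2.030 | 94.2% | 3.6% |
| 14 | 2.160 | 92.8% | 10.2% |
| 12 | 2.201 | 92.4% | 12.3% |
| 9 | 2.306 | 91.4% | 17.7% |
| 7 | 2.447 | 90.2% | 24.8% |
| 5 | 2.776 | 87.8% | 41.7% |
| 3 | 4.303 | 81.1% | 119.5% |

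**On the UNS scale.** The protocol synopsis sizes the trial on a 3-point difference, and SAP 4.2 on a standardized difference of 0.5. Together they imply SD = 3/0.5 = 6, used here as an assumption. The half-width is multiplier × 6/√n:
- n = 36: 1.960 × 1 = 1.96 points, against 2.030 × 1 = 2.03 under t.
- n = 9: 1.960 × 2 = 3.92, against 2.306 × 2 = 4.61.
- n = 7: 1.960 × 2.268 = 4.44, against 2.447 × 2.268 = 5.55.

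**How many cells.** The four factors have 2 + 2 + 4 + 2 = 10 levels, which makes 20 subgroup-by-arm cells per visit. Eight of them are age or sex cells, where about 14 placebo patients or more are expected. Only some of the BMI and narcolepsy-type cells could be smaller than that.

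**The case against.** The strongest reply is that no affected table can be pointed to. The interval is optional in 4.1.2 and absent from the default statistics, and the UNS subgroup sentence does not ask for one. Where the SAP does request an interval, it is for a between-group estimate or an odds ratio, not for an arm mean in a subgroup. The optional wording also leaves room to omit intervals in tiny cells. All of this stands. A reader might infer that every descriptive interval in the report will be wrong, or that many small-cell intervals are planned. The documents support neither: subgroup descriptives are explicit only for the UNS, and the table shells are not available.

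Two further replies stand in part. The t interval is itself exact only for normal data, and the UNS is a bounded integer score from 0 to 44, so t is an improvement rather than a guarantee at n = 3 to 5. And because n and SD are printed beside each mean, a reader can recompute any interval.

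A last reply is that the phrase may mean no more than normal theory, which would include t limits. That strains the text: the standard normal is a specific distribution whose quantile is 1.96. If normal theory was meant, the same edit removes the ambiguity.

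**Conclusion.** The rule as written is wrong for a mean with an estimated SD, and nothing else in the SAP corrects it. Its demonstrated reach is small. For whole arms the loss of coverage is less than one percentage point. If intervals are printed in the UNS subgroup tables, assumed placebo cells of about 7 to 14 patients would have coverage of about 90% to 93%, and any cell of 5 or fewer 88% or less. These figures rest on normal data, on the planned 36 and 72 patients, and on cell sizes that the documents do not give for BMI class or narcolepsy type.

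A reader might also infer that the trial's main result is touched. It is not. The treatment-effect interval and p-value for the UNS come from the mixed ANCOVA after multiple imputation, combined by Rubin's rules (SAP 4.1.3.1, 4.1.4.1 and 4.5.3.1.1), and the fixed sequence in 4.1.3.2 does not use descriptive intervals. This is a minor correction that would be nice to have.

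**What to change.** In SAP 4.1.2, replace the parenthesis naming the standard normal distribution with: Student t distribution with n-1 degrees of freedom, for descriptive confidence intervals of means. Optionally, add a minimum n below which no interval is shown.

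The cost is one phrase in the SAP. The edit needs no new data and changes no test. If no descriptive interval is ever printed, it does no harm.
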